2.3.1 Treatment Assignment and Randomization/Stratification Procedures

Cohorts

Number	Name	Description
1	Prostate Cancer Patients	Patients with chemotherapy naïve metastatic castrate-resistant prostate cancer

Short Title: Enzalutamide Vaccine in mCRPC

Version Date: 03/29/2022

Arms

Number	Name	Description
1	A	Enzalutamide alone
2	B	Enzalutamide with PSA-TRICOM

Stratifications

Name	Distinct Options	Notes
Prior Immunotherapy	Yes No	

Randomization and Arm Assignment

Patients must be registered with Central Registration Information Services within 24 hours after signing the consent. All Patients on study will be directly assigned to cohort 1.

Patients in cohort 1 will be randomized within 24 hours after registration. Block randomization will be used to randomly assign patients in a 1:1 manner between arms A and B. Randomization will be stratified by prior immunotherapy used as cancer treatment.

For randomization, authorized staff should call [contact] between the hours of 8:30 a.m. and 5:00 p.m., Monday through Friday. A recorder is available during non-working hours.

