5.3.2 Definitions

Evaluable for toxicity: All patients will be evaluable for toxicity from the time of their first treatment with enzalutamide with or without PSA-TRICOM.

Evaluable for objective response:

All of the patients who met the eligibility criteria (with the possible exception of those who received no study medication) are evaluable for response. Patients that have: progressive disease, early death from malignant disease, early death from toxicity, early death because of other cause, or unknown (not assessable, insufficient data) should be considered to have a treatment failure (disease progression). Thus, an incorrect treatment schedule or drug administration does not result in exclusion from the analysis of the response rate.

Evaluable Non-Target Disease Response: Patients who have lesions present at baseline that are evaluable but do not meet the definitions of measurable disease, have received at least one cycle of therapy, and have had their disease re-evaluated will be considered evaluable for non-target disease. The response assessment is based on the presence, absence, or unequivocal progression of the lesions.

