5.3.7 Time to Progression

Time to progression (TTP) is defined as the duration of time from start of treatment to time of disease progression.

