9 STATISTICAL CONSIDERATIONS

The primary objective is to determine if PSA-TRICOM combined with enzalutamide will increase time to progression in chemotherapy-naïve metastatic castration resistant prostate cancer patients compared to enzalutamide alone.

Secondary objectives include determining if PSA-TRICOM combined with enzalutamide will increase overall survival and/ or delay PSA progression compared to enzalutamide alone, and. Tumor growth rates at various time points will also be determined and compared as a secondary objective.

Exploratory objectives include comparing the immune response in patients between the two arms. Immune response evaluation will include CD4 cells, CD 8 cells, PSA-specific T-cells, natural killer cells, Regulatory T-cells, Regulatory T-cell function, cytokines, naïve thymic emigrants. The study will also aim to determine the association between immunologic parameters and clinical outcomes

The study is based on an assumption of a median time to progression of 10 months in chemotherapy-naïve mCRPC patients. Should the PREVAIL trial results be reported prior to the opening of this trial, and if they are substantially different from this estimate, adjustments in this plan will be made accordingly. The primary endpoint will be the comparison of the Kaplan-Meier curves for the two arms using a stratified log-rank test. The trial will be conducted using a phase 2.5 design (one tailed 0.10 alpha level test) [41].

If we assume that the arms will have time to progression medians of 10 vs. 18 cycles (which would have hazards of 0.0693 and 0.0385, respectively, and a hazard ratio of 1.80), and if patients are accrued for 36 months and the last one enrolled is followed for up to 12 more months (48 months total follow-up from time of enrolling first patient), and a total of 52 events are observed, then 36 patients per arm provides 80% power to compare the two arms.

Patients will be stratified based on previous immunotherapy used as cancer treatment.

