Survival will be compared between the two arms, as a secondary endpoint, using Kaplan-Meier curves and a stratified log-rank test. Continuous parameters will be compared between the two arms using appropriate non-parametric tests, such as a Wilcoxon rank sum test. Immune outcomes and clinical outcomes will be compared using appropriate measures, such as Spearman correlation, Fisher's exact test, or Wilcoxon rank sum test. All secondary outcomes will be reported without formal adjustment for multiple comparisons but in the context of the number of such tests performed.

In order to allow for a small number of inevaluable patients, up to 76 total patients may be enrolled in order to yield 72 total evaluable patients. If the study is able to accrue approximately 2 patients per month, then accrual can be completed in approximately 3 years.

This projected accrual time frame is based on a previous trial in mCRPC which recently enrolled at the NCI. Trial 11-C-0195 enrolled 52 patients in under 2 years, therefore it would be feasible to accrue the number of patients required in this design.

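### The TTP clock starts at treatment rather than randomisation, and the evaluable patients on whom the comparison is sized are not defined for TTP

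*Combined protocol and SAP*

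**What the plan says.** Section 2.3.1 has patients registered within a day of consent and then randomised: "Patients in cohort 1 will be randomized within 24 hours after registration". Section 5.3.7 starts the primary endpoint later; TTP is "defined as the duration of time from start of treatment to time of disease progression". The baseline work-up in section 2.4 is tied to treatment start (a 16-day window), and I found no maximum interval from randomisation to first dose.

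Section 9 gives the primary test as a "comparison of the Kaplan-Meier curves for the two arms using a stratified log-rank test", run as a "one tailed 0.10 alpha level test", and states that "36 patients per arm provides 80% power to compare the two arms". It then allows for losses: "up to 76 total patients may be enrolled in order to yield 72 total evaluable patients". The 72 is the 36 per arm of the power statement. Section 9 names no analysis population, and I found no intention-to-treat statement elsewhere.

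Evaluability is defined only in section 5.3.2, for toxicity, objective response and non-target disease. The response definition reads: "All of the patients who met the eligibility criteria (with the possible exception of those who received no study medication) are evaluable for response".

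**The concern.** Randomisation protects the comparison only if the groups compared are the groups randomised. Here the primary endpoint is undefined for a randomised patient who never starts treatment, so he is removed by the definition itself. If the response wording of section 5.3.2 is borrowed for TTP, patients later judged ineligible can go too. Both decisions come after the arm is assigned. The comparator is enzalutamide alone, with no placebo vaccine; blinding is mentioned only for counting ELISPOT wells, so open-label conduct is an inference, but a safe one.

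The allowance is small, 4 of 76 patients (4/76 = 5.3%). But the test is one-sided at 0.10 with about 52 events, so a few patients removed for reasons linked to outcome can shift the result in either direction. Nothing in the plan says which patients may be removed, by whom, or with what knowledge of outcome.

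**Working it through.** **Step 1. The plan's own figure.** Inputs from section 9: 52 events, "a hazard ratio of 1.80", one-sided alpha 0.10, 1:1 allocation. Schoenfeld power is Φ(√52/2 × ln 1.80 − 1.2816) = Φ(3.606 × 0.5878 − 1.2816) = Φ(0.838) = 0.799, against the stated 80%. The same formula needs 53 events for 80%, against 52 stated. The sample size reproduces.

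**Step 2. Events available.** Assume exponential TTP with medians of 10 and 18 months, uniform accrual over 36 months, and a data cut at 48 months. (Section 9 labels the control median months in one paragraph and cycles in the next; the hazard ratio is unaffected.) The probability of an event is 1 − [exp(−12λ) − exp(−48λ)]/(36λ). With λ = 0.0693 this is 0.840; with λ = 0.0385 it is 0.659.
- 36 per arm: 36 × (0.840 + 0.659) = 54.0 events, power 0.810.
- 38 per arm: 38 × (0.840 + 0.659) = 57.0 events, power 0.826.

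If the analysis is triggered at exactly 52 events, power is 0.799 in both cases. Analysing everyone randomised therefore loses no power, provided that all are followed for progression.

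**Step 3. What exclusions could do.** The documents give no exclusion pattern, so these are assumed scenarios. Simulation: 38 per arm, control median 10 months, accrual and cut as above, unstratified log-rank test, 10,000 runs (simulation standard error about 0.003 at 0.10). The hazard ratio is vaccine over control, with no true effect.

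| Patients removed | One-sided error | Mean estimated HR |
|---|---|---|
| None | 0.099 | 1.00 |
| 2 per arm, at random | 0.104 | 1.00 |
| 1, 2 or 4 in arm B, at random from the poorer-outcome half | 0.115, 0.136, 0.182 | 0.98, 0.96, 0.91 |
| 1, 2 or 4 earliest progressors in arm B | 0.129, 0.152, 0.232 | 0.97, 0.94, 0.88 |
| 2 or 4 earliest progressors in arm A | 0.064, 0.038 | 1.07, 1.14 |

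A separate run of 20,000 replicates removed 1, 2, 3 or 4 arm B patients chosen at random among those progressing before 3 months. It gave 0.126, 0.152, 0.184 and 0.215, from a base of 0.102. Under the plan's effect (HR 1.80), removing the 4 earliest progressors in arm A cuts power from 0.82 to 0.66.

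**The case against.** Four points can be made in the plan's defence.

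First, a reader might infer that the plan prescribes a primary analysis restricted to evaluable patients. It does not say so. The sentence about 76 and 72 is an enrolment ceiling, and the log-rank sentence names no set. This stands: the defect is an unspecified population together with a time origin that excludes the untreated, not a stated per-protocol analysis.

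Second, the inflated error rates remove patients because they progressed early, and section 5.3.2 points the other way. For response, it counts progression, early death and insufficient data as treatment failure, and it does not allow a wrong schedule or administration as a reason to exclude. An eligible, treated early progressor would therefore be kept. Only untreated or ineligible patients are exposed, and nothing links them to poor outcome. This stands as a limit on size. It does not remove the exposure, because the wording was written for response and no rule covers TTP.

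Third, a reader might infer that treatment starts later in the vaccine arm. The documents do not support this. Section 3.3.2.1 allows a 14-day delay in enzalutamide, which both arms receive, and nothing says that vaccine logistics hold up the first dose. If arm B alone were delayed by 0.25 to 1.0 month with the progression process unchanged, the modelled error would be 0.088 to 0.055, a bias against the vaccine. I do not rely on this.

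Fourth, a reader might take the early-death wording in section 5.3.2 as authority to count every death as a TTP event. That wording concerns objective response. Applying it to all deaths would turn TTP into progression-free survival, which changes the primary endpoint and is a separate choice.

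**Conclusion.** The point holds in limited form. By the definition in section 5.3.7, randomised but untreated patients cannot enter the primary comparison; ineligible patients may be left out; and the evaluable patients behind the power statement are undefined for TTP.

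The consequence depends on assumptions that the documents neither make nor exclude. With 1 to 4 outcome-related exclusions, all in arm B, one-sided error is roughly 0.12 to 0.23; the top value needs the 4 earliest progressors to be the ones removed. With 4 in arm A, error is about 0.04 and power drops to about 0.66. With exclusions unrelated to outcome, error stays near 0.10. These figures assume exponential TTP, no loss to follow-up and an unstratified test, whereas the plan stratifies by prior immunotherapy.

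This should be fixed because the remedy is cheap and removes the question. It does not show that the trial's result is biased, and no figure in section 9 is wrong on this account.

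**What to change.** In sections 5.3.7 and 9, state that:
- the primary stratified log-rank test includes all randomised patients in the arm assigned;
- TTP runs from the date of randomisation;
- the evaluable, from-treatment analysis is a sensitivity analysis, with evaluable defined for TTP and every exclusion listed by arm with its reason;
- death before documented progression is handled by a stated rule, with an analysis of progression or death reported as sensitivity. The primary endpoint stays TTP.

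Section 6.5.2 records that accrual has closed, so the change should be dated and should say whether outcomes by arm had been seen.

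No extra patients are needed, and the randomisation dates should already be on file. There are two small downsides. Untreated patients dilute the effect slightly. They may also add little information: scans follow treatment cycles (section 3.4) and patients leave the study about 30 days after treatment ends (section 3.6.2), so some would be censored early. A patient censored at entry leaves the log-rank statistic unchanged, so the rise in power from 0.810 to 0.826 is an upper limit that requires full follow-up.

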9.1 EARLY STOPPING RULE

After 50% of the patients (36 total) have been enrolled and followed potentially for 12 months, if the vaccine arm demonstrates the same or worse time to progression than the enzalutamide alone arm, that is, if the arms substantially overlap or if the enzalutamide alone arm appears to have better outcomes than the combination arm, then no further patients will be accrued.

10 COLLABORATIVE AGREEMENTS

10.1 AGREEMENT TYPE

10.1.1 Cooperative Research and Development Agreement (CRADA):

- This study is conducted under a CRADA with Bavarian Nordic (CRADA # 02377)
- This study is conducted under a CRADA with Astellas and Medivation (CRADA # 02859)

10.1.2 Material Transfer Agreement

- A Material Transfer Agreement is in place with Epic Sciences for the studies discussed in section [4.1.4](#)
- A Material Transfer Agreement is in place with The Cleveland Clinic Foundation for the studies discussed in section [4.1.6](#)

11 HUMAN SUBJECTS PROTECTIONS

11.1 RATIONALE FOR SUBJECT SELECTION

11.1.1 Selection Based on Ethnicity, and Race

Subjects from all racial/ethnic groups are eligible for this study if they meet the eligibility criteria. To date, there is no information that suggests that differences in drug metabolism or disease response would be expected in one group compared with another. Efforts will be made to extend accrual to a representative population, but in this preliminary study, a balance must be struck between patient safety considerations and limitations on the number of individuals exposed to potentially toxic and/or ineffective treatments on one hand and the need to explore ethnic aspects of clinical research on the other hand. If differences in outcome that correlate with ethnic identity

are noted, accrual may be expanded or a follow-up study may be written to investigate those differences more fully. Women are not eligible for this protocol as this disease occurs only in men.

11.1.2 Justification for Exclusions

Due to impaired cellular immunity with the concomitant increased risk of serious side effects from vaccinations with infectious agents, the Centers for Disease Control and Prevention recommends that HIV infected patients be excluded, in addition, patients with chronic hepatitis infection, including B and C, because of potential immune impairment will be excluded.

11.2 PARTICIPATION OF CHILDREN

Because no dosing or adverse event data are currently available on the use of PSA-TRICOM Vaccine or enzalutamide in patients <18 years of age, children are excluded from this study, but may be eligible for future pediatric trials.

11.3 PARTICIPATION OF SUBJECTS UNABLE TO GIVE CONSENT

Adults unable to give consent are excluded from enrolling in the protocol. However, re-consent may be necessary and there is a possibility, though unlikely, that subjects could become decisionally impaired. For this reason and because there is a prospect of direct benefit from research participation (section 11.4), all subjects will be offered the opportunity to fill in their wishes for research and care, and assign a substitute decision maker on the “NIH Advance Directive for Health Care and Medical Research Participation” form so that another person can make decisions about their medical care in the event that they become incapacitated or cognitively impaired during the course of the study. Note: The PI or AI will contact the NIH Ability to Consent Assessment Team (ACAT) for evaluation to assess ongoing capacity of the subjects and to identify an LAR, as needed.

Please see section 11.5.1.

11.4 EVALUATION OF BENEFITS/RISKS/DISCOMFORTS

11.4.1 Alternative Approaches or Treatments

Patients will be consented verbally and in writing regarding the risks and benefits of this trial, the treatment requirements, and alternative approaches to entering on this trial.

11.4.2 Procedure for Protecting Against or Minimizing any Potential Risks

All care will be taken to minimize side effects, but they can be unpredictable in nature and severity. This study may involve risks to patients, which are currently unforeseeable. All patients will have blood tests, examinations and scans as described in the protocol evaluation (Section 3.4 Study Calendar). Patients will also be required to have a local physician to provide long-term care and to monitor for complications. If patients suffer any physical injury as a result of the participation in this study, immediate medical treatment is available at the Clinical Center, National Cancer Institute, Bethesda, Maryland. Although no compensation is available, any injury will be evaluated and treated in keeping with the benefits or care to which patients are entitled under applicable regulations.

11.4.3 Provisions for Monitoring Data Collection to Ensure Safety of Subjects

As information is gathered from this trial, clinical results will be shared with patients as they become available. Laboratory and clinical data will be frequently gathered and any new significant

finding(s) found during the course of the research, which may affect a patient's willingness to participate further, will be explained. Confidentiality of information concerning participants will be maintained, including in all publications and presentations resulting from this study. Names of participants and/or material identifying participants will not be released without permission, except as such release is required by law. Records at the National Cancer Institute are maintained according to current legal requirements, and are made available for review, as required by the Food and Drug Administration or other authorized users, only under the guidelines established by the Federal Privacy Act.

11.5 CONSENT PROCESS AND DOCUMENTATION

The informed consent document will be provided as a physical or electronic document to the participant or consent designee(s) as applicable for review prior to consenting. A designated study investigator will carefully explain the procedures and tests involved in this study, and the associated risks, discomforts, and benefits. For the apheresis for research in the protocol, the patient will consent at the time of the procedures. If the patient refuses the apheresis at that time, the refusal will be documented in the medical record and in the research record.

In order to minimize potential coercion, as much time as is needed to review the document will be given, including an opportunity to discuss it with friends, family members, and/or other advisors, and to ask questions of any designated study investigator. A signed informed consent document will be obtained prior to entry onto the study.

The initial consent process as well as re-consent, when required may take place in person or remotely (e.g., via telephone or other NIH approved remote platforms used in compliance with policy, including HRPP Policy 303) per discretion of the designated study investigator and with the agreement of the participant/consent designee(s). Whether in person or remote, the privacy of the subject will be maintained. Consenting investigators (and participant/consent designee, when in person) will be located in a private area (e.g., clinic consult room). When consent is conducted remotely, the participant/consent designee will be informed of the private nature of the discussion and will be encouraged to relocate to a more private setting if needed.

Consent will be documented with required signatures on the physical document (which includes the printout of an electronic document sent to participant) or as described below, with a manual (non-electronic) signature on the electronic document. When required, witness signature will be obtained similarly as described for the investigator and participant.

Manual (non-electronic) signature on electronic document:

When a manual signature on an electronic document is used for the documentation of consent at the NIH Clinical Center, this study will use the following to obtain the required signatures:

- Adobe platform (which is not 21 CFR Part 11 compliant); or,
- iMedConsent platform (which is 21 CFR Part 11 compliant)

During the consent process, participants and investigators will view individual copies of the approved consent document on screens at their respective locations (if remote consent); the same screen may be used when in the same location but is not required.

Both the investigator and the participant will sign the document using a finger, stylus or mouse.

Note: Refer to the CCR SOP PM-2, Obtaining and Documenting the Informed Consent Process for additional information (e.g., verification of participant identity when obtaining consent remotely) found [here](#).

11.5.1 Consent Process for Adults Who Lack Capacity to Consent to Research Participation

For participants addressed in section [11.3](#), an LAR will be identified consistent with Policy 403 and informed consent obtained from the LAR, as described in Section [11.5.1](#).

12 REGULATORY AND OPERATIONAL CONSIDERATIONS

12.1 STUDY DISCONTINUATION AND CLOSURE

This study may be temporarily suspended or prematurely terminated if there is sufficient reasonable cause. Written notification, documenting the reason for study suspension or termination, will be provided by the suspending or terminating party to study participants, investigator, funding agency, the Investigational New Drug (IND) sponsor and regulatory authorities. If the study is prematurely terminated or suspended, the Principal Investigator (PI) will promptly inform study participants, the Institutional Review Board (IRB), and sponsor and will provide the reason(s) for the termination or suspension. Study participants will be contacted, as applicable, and be informed of changes to study visit schedule.

Circumstances that may warrant termination or suspension include, but are not limited to:

- Determination of unexpected, significant, or unacceptable risk to participants
- Demonstration of efficacy that would warrant stopping
- Insufficient compliance to protocol requirements
- Data that are not sufficiently complete and/or evaluable
- Determination that the primary endpoint has been met
- Determination of futility

Study may resume once concerns about safety, protocol compliance, and data quality are addressed, and satisfy the sponsor, IRB and as applicable, Food and Drug Administration (FDA).

